APPENDIX 4 DIAGNOSTIC CRITERIA FOR DRUG AND ALCOHOL ABUSE

The following is taken from the Diagnostic and Statistical Manual of Mental Disorders, 4th edition:

DIAGNOSTIC CRITERIA FOR PSYCHOACTIVE SUBSTANCE DEPENDENCE

A maladaptive pattern of substance use, leading to clinically significant impairment or distress as manifested by 3 (or more) of the following, occurring at any time in the same 12-month period:

- 1) Tolerance, as defined by either of the following:
 - a) A need for markedly increased amounts of the substance to achieve intoxication or desired effect
 - b) Markedly diminished effect with continued use of the same amount of the substance
- 2) Withdrawal, as manifested by either of the following:
 - a) The characteristic withdrawal syndrome for the substance
 - b) The same (or closely related) substance is taken to relieve or avoid withdrawal symptoms
- 3) The substance is often taken in larger amounts or over a longer period than was intended
- 4) There is a persistent desire or unsuccessful efforts to cut down or control substance use
- 5) A great deal of time is spent in activities necessary to obtain the substance (eg, visiting multiple doctors or driving long distances), use the substance (eg, chain-smoking), or recover from its effects
- 6) Important social, occupational, or recreational activities are given up or reduced because of substance use
- 7) The substance use is continued despite knowledge of having a persistent or recurring physical or psychological problem that is likely to have been caused or exacerbated by the substance (eg, current cocaine use despite recognition of cocaine-induced depression, or continued drinking despite recognition that an ulcer was made worse by alcohol consumption.)

CRITERIA FOR SEVERITY OF PSYCHOACTIVE SUBSTANCE DEPENDENCE

Mild: Few, if any, symptoms in excess of those required to make the diagnosis, and the symptoms result in no more than mild impairment in occupational functioning or in usual social activities or relationships with others.

Moderate: Symptoms or functional impairment between “mild” and “severe.”

Severe: Many symptoms in excess of those required to make the diagnosis, and the symptoms markedly interfere with occupational functioning or with usual social activities or relationships with others.

In Partial Remission: During the past 6 months, some use of the substance and some symptoms of dependence.

In Full Remission: During the past 6 months, either no use of the substance, or use of the substance and no symptoms of dependence.

DIAGNOSTIC CRITERIA FOR PSYCHOACTIVE SUBSTANCE ABUSE

- A. A maladaptive pattern of psychoactive substance use, leading to clinically significant impairment or distress as manifested by 1 (or more) of the following, occurring at any time in the same 12-month period:
- 1) Recurrent substance use resulting in a failure to fulfill major role obligations at work, school, or home (eg, repeated absences or poor work performance related to substance use; substance-related absences, suspensions, or expulsions from school, neglect of children or household)
 - 2) Recurrent substance use in situations in which it is physically hazardous (eg, driving an automobile or operating a machine when impaired by substance use)
 - 3) Recurrent substance-related legal problems (eg, arrests for substance-related disorderly conduct)
 - 4) Continued substance use despite having persistent or recurrent social or interpersonal problems caused or exacerbated by the effects of the substance (eg, arguments with spouse about consequences of intoxication, physical fights)
- B. The symptoms have never met the criteria for substance dependence for this class of substance

APPENDIX 5 REPRESENTATIVE STANDARD HIGH FAT AND HIGH CALORIE MEAL

STANDARD HIGH-FAT AND HIGH-CALORIE MEAL

The standard FDA high-fat breakfast of 918 kcal consists of:

- 2 fried eggs (in 15 g butter/margarine) (approximately 100 g)
- 1 portion of bacon (40 g)*
- 1 portion of fried potatoes (115 g)
- 2 slices of (toasted) (wheat) bread with 15 g margarine
- 1 glass of high fat milk (240 mL)

* For vegetarians bacon may be replaced by brie 60+

The total of 918 kcal (vegetarian version 915 kcal) can be broken down as follows:

- 39 g protein = 156 kcal
- 59 g fat = 527 kcal
- 59 g carbohydrates = 235 kcal

### 3.0 Introduction

This Statistical Analysis Plan (SAP) describes the statistical methods that will be used during the analysis and reporting of data collected under Bristol-Myers Squibb Research and Development (BMS) Protocol IM024 005.

This SAP should be read in conjunction with the study protocol and electronic case report form (eCRF). This version of the plan has been developed using the final protocol version 1.0 dated 21-Sep-2017 (including all amendments up to this protocol date) and the final eCRF(s) dated 12-Feb-2018 (single ascending dose [SAD]) and 01-Jun-2018 (multiple ascending dose [MAD]).

An approved and signed SAP is a requirement for database lock. An approved SAP is also required for unblinding of the study treatments.

This SAP only covers the results that will be processed by the PRA Early Development Services (EDS) Biostatistics Department.

PRA EDS will perform the pharmacokinetic (PK), pharmacodynamic (PD), and safety and tolerability evaluation.

This SAP was written after the clinical study was terminated due to non-clinical findings. The study was stopped after completion of Part A, Cohorts A1 – A4 and during dosing of the cohort A5 and the first cohort of Part B, B1. Cohort A6 and bioavailability (BA) / food effect (FE) cohort in Part A, cohorts B2-B4 in Part B and Part C were not conducted. In this SAP, only analyses applicable for the data collected are included.

This SAP supersedes the statistical considerations identified in the protocol; where considerations are substantially different, they will be so identified. Any post-hoc or unplanned analyses, or significant changes from the planned analysis in this SAP, will be clearly identified in Section 9.8.2 of the clinical study report (CSR). Changes to planned analyses do not require an updated SAP but will be included in the CSR if significant.

### 4.0 Changes from Previous Version of Approved SAP

This is the first version of the SAP.

### 5.0 Study Objectives

#### 5.1 Primary

To evaluate the safety, tolerability and PK of escalating single and multiple ascending doses of BMS-986251 in healthy subjects, and of multiple doses of BMS-986251 in patients with moderate-to-severe psoriasis.

##### 5.1.1 Primary Endpoint

###### Safety and tolerability

- Number and percent of subjects that experience the following: SAE, death or an AE leading to study discontinuation, during the study participation or up to 1 month post discontinuation of dosing or last participation in the study for SAE.
- Number and percent of subjects with potentially clinically significant changes in ECG parameters, vital signs, or clinical laboratory parameters from Day 1 through the final follow visit.

Other safety measures collected during the study are not considered among the primary endpoint and will be summarized as safety endpoints.

###### Pharmacokinetics

- Plasma concentrations of BMS-986251 and derived PK parameters as applicable

## 5.2 Secondary

- To evaluate the PD of escalating single and multiple ascending doses of BMS-986251 in healthy subjects, and of multiple doses of BMS-986251 in patients with moderate-to-severe psoriasis.
- To evaluate the oral bioavailability (BA) of an oral suspension of BMS-986251 relative to a liquid dosage form at a single dose level in healthy subjects.
- To evaluate the effect of a high-fat meal on the PK of an oral suspension of BMS-986251 at a single dose level in healthy subjects.
- To explore clinical effects of multiple doses of BMS-986251 in patients with moderate-to-severe psoriasis.

### 5.2.1 Secondary Endpoint

- The percentage ex-vivo inhibition (I) of interleukin (IL)-17 secretion in whole blood and derived PD parameters
- Plasma concentrations of BMS-986251 following oral suspension and derived PK parameters as applicable
- Plasma concentrations of BMS-986251 following high-fat meal and derived PK parameters as applicable

## 6.0 Planned Study Design

This is a double-blind, placebo-controlled, randomized SAD and MAD study in 3 parts in a planned number of approximately 103 participants: 88 healthy subjects and 15 patients with psoriasis. The present study is designed to evaluate the safety and tolerability, PK, PD and efficacy of BMS-986251. Part A and B are planned to enroll healthy subjects and is conducted at a single site. Part C was planned to enroll patients with psoriasis and to be conducted as a multi-center study in multiple countries. Part C was not executed due to study termination.

[figure not shown]
Part A is a SAD study in a planned number of 6 sequential cohorts of 8 healthy subjects (6 active + 2 placebo) each, receiving single escalating oral doses of BMS-986251. In the 1st cohort, sentinel dosing will be employed (1 active + 1 placebo, followed after 72 hours by the remaining subjects of the 1st cohort [5 active + 1 placebo]). In addition to the 6 ascending dose cohorts, a cohort of 8 healthy subjects (8 active) will be included to assess the relative BA of an oral suspension (under development; representative for the solid dosage form to be used in Part C) compared to the solution formulation, and to evaluate the effect of food on the BA of the oral suspension in a 3-period sequential design (BA/food effect [FE] cohort).

Part B is a MAD study in a planned number of 4 sequential cohorts of 8 healthy subjects (6 active + 2 placebo) each, receiving daily oral doses of escalating BMS-986251 for 2 weeks.

Part C is a multiple dose part in one cohort of 15 patients with moderate-to-severe psoriasis (12 active + 3 placebo), treated for 2 weeks, with a potential extension to 12 weeks by protocol amendment. Per protocol amendment, this study part may be extended with further cohorts, receiving lower repeated BMS-986251 doses than Cohort C1. A decision to extend the study with (a) lower-dosed cohort(s) will be based on the efficacy/safety balance of the 1st patient cohort. A high therapeutic response or, alternatively, poor safety or tolerability observed in the 1st patient cohort may be the basis to amend the study protocol for extension to a lower dosed cohort.

An overview of the study is provided in Figure 1, Table 1, Table 2 and Table 3.

**Figure 1 Study Design Schematic**

A = active; BA = bioavailability; FE = food effect; MAD = multiple ascending dose; NHV = healthy volunteers; P = placebo; PD = pharmacodynamics; PK = pharmacokinetics; Pso = psoriasis; SAD = single ascending dose; wk = week

Note: SAD Cohort A1 will have a sentinel dosing design with 2 subjects (1 active and 1 placebo) dosed 72 hours prior to the remaining subjects in the cohort.

**Table 1 Part A Dose Cohorts**

Cohort	Number of Subjects (Active / Placebo)	Period	Dose of BMS-986251	Fasted / Fed	Formulation
A1	1 / 1 (sentinel group)	1	2 mg	Fasted	Oral solution
	5 / 1	1	2 mg	Fasted	Oral solution
A2	6 / 2	1	6 mg	Fasted	Oral solution
A3	6 / 2	1	15 mg	Fasted	Oral solution
A4	6 / 2	1	30 mg	Fasted	Oral solution
A5	6 / 2	1	60 mg	Fasted	Oral solution
A6	6 / 2	1	120 mg	Fasted	Oral solution
A7 (BA/FE)	8	1	tbd	Fasted	Oral solution
		2	tbd	Fasted	Oral suspension (under development)
		3	tbd	Fed	Oral suspension (under development)

BA = bioavailability; FE = food effect; tbd = to be determined

Doses maybe adjusted based on data obtained in previous cohorts.

**Table 2 Part B Dose Cohorts**

Cohort	Subjects (Active / Placebo)	Dose of BMS-986251	Duration	Fasted/Fed	Formulation
B1	6 / 2	6 mg QD	14 days	Fasted	Oral solution
B2	6 / 2	tbd QD	14 days	Fasted	Oral solution
B3	6 / 2	tbd QD	14 days	Fasted	Oral solution
B4	6 / 2	60 mg QD	14 days	Fasted	Oral solution

QD = once daily; tbd = to be determined upon reviewed data

Doses maybe adjusted based on data obtained in previous cohorts.

**Table 3 Part C Dose Cohort**

Cohort	Subjects (Active / Placebo)	Dose of BMS-986251	Duration	Fasted/Fed	Formulation
C1	12 / 3	60 mg QD	14 days	tbd	Oral tablet

QD = once daily; tbd = to be determined upon reviewed data

Dose may be adjusted based on data obtained in previous study parts.

## 6.1 Sample Size Considerations

### Part A and B – SAD and MAD cohorts

The current design of 8 subjects per cohort with 6 subjects assigned to active treatment is a commonly used design for SAD and MAD studies and is considered sufficient to achieve the study objectives. Although this number of is not based on statistical power considerations, administration of BMS-986251 to 6 subjects in each dose cohort provides approximately 80% probability of observing at least one occurrence of any AE which would occur with approximately 24% incidence in the population from which the sample is drawn.

### Part A – BA/FE cohort

The planned number of 8 subjects on active treatment to be enrolled in the BA/FE cohort (in which BA and FE of an oral suspension will be evaluated in a 3-period sequential design), has not been based on formal statistical sample size calculations. This number of subjects is a commonly accepted number of subjects for this type of exploratory study and is considered sufficient to achieve the study objectives.

### Part C – Psoriasis patients

Like Parts A and B, Part C is also an exploratory study. Therefore, no formal statistical sample size calculation has been performed and the sample size is not based on a power calculation. The planned number of 15 subjects with 12 subjects on active treatment is a commonly accepted number of subjects for this type of exploratory study. Formal statistical hypotheses were not set up. Any statistical test performed will be exploratory.

## 6.2 Randomization

Within each cohort (excluding the BA/FE cohort of Part A), subjects will be randomized to receive either BMS-986251 or placebo. All subjects who sign informed consent and are enrolled (including those not subsequently randomized or treated) will be assigned sequential subject numbers. Eligible subjects will be randomized according to a computer-generated randomization scheme. Subjects in Cohort A7 in Part A will be assigned sequential subject numbers in the order of enrollment. Eligible subjects will be treated in accordance with the study design.

---

#### Part A, SAD in Healthy Volunteers:

Approximately 48 subjects (8 in each cohort) enrolling in Cohorts A1 to A6 will be randomized to BMS-986251 or matching placebo in a 3:1 randomization ratio. All subjects in BA/FE Cohort A7 will receive BMS-986251.

#### Part B, MAD in Healthy Volunteers:

Approximately 32 subjects will be enrolled in 4 dose cohorts during the MAD study. Each dose cohort will randomize 8 subjects in a 3:1 ratio to receive BMS-986251 or matching placebo.

#### Part C, Multiple Dosing in Psoriasis Patients:

Approximately 15 subjects in one planned dose cohort will be randomized in a randomization ratio of 4:1 to receive BMS-986251 or matching placebo.

## 7.0 Overview of Planned Analysis

### 7.1 Changes from Protocol

This study was terminated on June 25, 2018 prior to completion of dosing in all planned cohorts and subjects within cohort. Following cohorts have been dosed before the termination:

#### Part A

Cohort A1 (2mg): n=8

Cohort A2 (6 mg): n=8

Cohort A3 (15 mg): n=8

Cohort A4 (30 mg): n=8

Cohort A5 (60 mg): n=4

#### Part B

Cohort B1 (3 mg QD): n=2 (dosing till Day 10)

Summary tables of disposition, demographics and adverse events will be provide for Part B, but data from Part B subjects will be presented in all listings with data for Part B.

Cohort A6 and BA/FE cohort in Part A, cohorts B2-B4 in Part B and Part C were not conducted.

### 7.2 Planned Analyses

#### 7.2.1 Preliminary Analysis

Interim PK blinded results were provided after each cohort to the study team. A non-project team member PK Scientist will be the only team member to have access to the unblinded results.

#### 7.2.2 Final Analysis

The full set of draft table, figures and listings (TFLs) will be provided after database lock. After comments have been incorporated on the draft TFLs, the TFLs will be finalized and incorporated in the CSR.

---

## 8.0 Definitions and General Analysis Methods

### 8.1 Analysis Data Presentation

#### 8.1.1 Rounding

In listings, data will be presented with the same precision as the original data. Derived data will be rounded for presentation purposes.

For all summaries (with the exception of PK), the mean will be presented to 1 decimal greater than the original data, the standard deviation (SD) to 2 decimals greater than the original data, and the median, minimum (min) and maximum (max) values will be presented to the same number of decimal places as the original data.

For PK summaries, mean, SD, median, min, and max values  $\geq 100$  will be presented as integers and values  $< 100 \geq 10$  will be presented with 1 decimal, Values  $< 10$  but  $\geq 1$  will be presented with 2 decimals, and Values  $< 1$  will be presented with 3 decimals. Ratios will be presented with 2 decimals. Coefficient of variation (%CV) will be presented with 1 decimal.

For listing presentation purposes, PK parameters will be rounded in the same manner as noted above for summaries. The Tmax will be reported with 2 decimals.

P-values will be reported to 4 decimal places; p-values less than 0.0001 will be reported as  $p < 0.0001$ .

Percentages will be rounded to 1 decimal, except 100% which will be displayed without any decimal places.

#### 8.1.2 Imputation

Unless otherwise noted (section 15.2.1 and 17.1.1), data will not be imputed.

#### 8.1.3 Descriptive Statistics

Unless otherwise indicated in specific data type sections, continuous variables will be summarized with the following descriptive statistics: n (number of observations), (arithmetic) mean, SD, median, min, and max.

Categorical data will be summarized with frequencies and percentages. Percentages by categories will be based on the number of subjects within a treatment group. Percentages will be rounded to 1 decimal, except 100% which will be displayed without any decimal places. Percentages will not be displayed for zero counts. Categories will be presented in the tables exactly as they appear in the eCRF / Database.

#### 8.1.4 Pooling

Summary statistics will be calculated by study part, treatment (and time point, if applicable). Placebo data will be pooled across cohorts in Part A for descriptive statistics.

#### 8.1.5 Unscheduled Measurements

Unscheduled measurements will be included in the listings. With the exception of unscheduled measurements used for baseline, unscheduled measurements will be excluded from the descriptive statistics and statistical analysis.

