8.5.2.4 Clinical Safety Laboratory Assessments

Investigators must document their review of each laboratory safety report. A local laboratory will perform the analyses and will provide reference ranges for these tests. Results of clinical laboratory tests performed on Day -1 must be available prior to first dosing.

Results of all laboratory tests required by this protocol must be provided to BMS, either recorded on the laboratory pages of the eCRF or by another mechanism as agreed upon between the Investigator and BMS (eg, provided electronically). In case of unexplained or unexpected clinical laboratory test values, the tests will be repeated as soon as possible and followed up until the results have returned to the normal range and/or an adequate explanation for the abnormality is found. The clinical laboratory will clearly mark all laboratory test values that are outside the normal range and the Investigator will indicate which of these deviations are clinically significant. Any abnormal laboratory test result considered clinically significant by the Investigator must be recorded on the appropriate AE page of the eCRF (Section [8.5.2.1.6](#)).

Samples for clinical laboratory will be taken in the fasted state (at least 4 hours).

Table 10 Clinical Laboratory Assessments

Hematology

Hemoglobin
Hematocrit
Total leukocyte count, including differential
Platelet count
Red blood cell count
Reticulocyte count

Chemistry

Aspartate aminotransferase (AST)	Sodium
Alanine aminotransferase (ALT)	Potassium
Total bilirubin	Chloride
Direct bilirubin	Calcium
Alkaline phosphatase	Inorganic phosphate
Lactate dehydrogenase (LDH)	Magnesium
Creatinine	Creatine kinase
Urea	Creatinine clearance (CLcr)- screening only
Uric acid	Cholesterol
Fasting glucose	Triglycerides
High sensitivity C-reactive protein (hs-CRP)	High-density lipoprotein (HDL)
Total protein	Low-density lipoprotein (LDL)
Albumin	

Urinalysis

Protein
Glucose
Blood
Leukocyte esterase
Specific gravity
pH
Microscopic examination of the sediment if blood, protein or leukocytes esterase are positive on the dipstick

Serology

Serum for hepatitis C antibody, HBsAg, and HIV-1 and -2 antibody (at screening only)
Quantiferon Gold test[®] for tuberculosis (TB) (at screening only)

Other Analyses

Urine test for alcohol (see [Table 1](#) through [Table 4](#))
Urine test for drugs of abuse (see [Table 1](#) through [Table 4](#))
Pregnancy test (females only; see [Table 1](#) through [Table 4](#))

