### 8.2 Analysis Data Definitions

#### 8.2.1 Baseline Definition

Unless otherwise stated, baseline for post-dose evaluations within each period is defined as the last observation recorded before the first study drug administration in each period. The last observation can be an unscheduled / repeated measurement.

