### 17.1.3 Laboratory Data

Clinical laboratory data will be presented using units from the study data tabulation model (SDTM) Controlled Terminology.

A descriptive statistics summary of continuous laboratory results for clinical chemistry, hematology and derived changes from baseline will be provided by treatment and scheduled time point.

Shift tables describing the change in clinical laboratory values from baseline to each post-dose scheduled time point (number and percentage of subjects) will also be provided by treatment. The following categories will be used: low, normal, and high.

All laboratory data will be listed by subject, including laboratory variables not listed in the protocol.

A separate listing of out-of-range values will also be provided. Normal ranges will be used directly from the clinical laboratory and will be included in the listings for reference.

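### SAP 8.1.5 keeps unscheduled post-dose values out of the primary count of subjects with potentially clinically significant changes and out of the laboratory shift table

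*SAP*

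**What the plan says.** SAP 8.1.5 has two parts. The first keeps the data visible: "Unscheduled measurements will be included in the listings". The second removes them from summaries: "With the exception of unscheduled measurements used for baseline, unscheduled measurements will be excluded from the descriptive statistics and statistical analysis". SAP 8.1.3, under the title of descriptive statistics, includes counts: "Categorical data will be summarized with frequencies and percentages".

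SAP 5.1.1 gives two primary safety components. One is based on events: "SAE, death or an AE leading to study discontinuation". The other is a subject-level count of measured values: "Number and percent of subjects with potentially clinically significant changes in ECG parameters, vital signs, or clinical laboratory parameters". Its window is Day 1 through the final follow-up, and it is not limited to scheduled visits. The same section places all other safety measures outside the primary endpoint.

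SAP 17.1.3 plans "Shift tables describing the change in clinical laboratory values from baseline to each post-dose scheduled time point". SAP 17.1.4 and 17.1.5 summarise vital signs and ECGs by scheduled time and plan no shift table for either.

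On the source of unscheduled values, Protocol 8.5.2.4 says: "In case of unexplained or unexpected clinical laboratory test values, the tests will be repeated as soon as possible". On baseline, SAP 8.2.1 says: "The last observation can be an unscheduled / repeated measurement".

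**The concern.** The endpoint covers a continuous period, but the rule admits only values on the visit grid. A liver test, QTcF or blood pressure that first crosses a threshold on a symptom-driven test, or during the follow-up of an unexpected result, falls inside the endpoint's window and outside the data allowed into the count.

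The protocol makes such tests routine, because unexpected laboratory results are to be repeated promptly and followed until they are normal or explained. At stake is whether a dose group is reported with no affected subjects or with some, on a primary endpoint in a first-in-human study with six active subjects per full cohort.

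**Working it through.** **Does the exclusion reach the primary count?**

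1. The second primary component is a number and percentage of subjects (SAP 5.1.1).
2. Frequencies and percentages are descriptive statistics (SAP 8.1.3).
3. Unscheduled post-dose measurements are excluded from descriptive statistics, and the only exception is for baseline (SAP 8.1.5).
4. No other section restores them for this component. SAP Appendix 4 lists no table for it, and the SAP gives no criteria for potentially clinically significant. Whoever builds the table would therefore apply 8.1.5 by default.

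**Direction.** Let S be a subject's scheduled post-dose values and U the unscheduled ones. If a subject counts when any value qualifies, everyone who qualifies on S alone also qualifies on S and U together. Dropping U can only lower the count or leave it unchanged. A repeat that merely confirms a scheduled abnormality changes nothing.

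**How thin is the schedule?** Protocol Table 20 allows 6 chemistry and 6 haematology samples per subject in Cohorts A1 to A6. Protocol Table 1 places one at screening and one on Day -1, so 6 − 2 = 4 are post-dose, through Day 11. Vital signs and ECGs are scheduled more often.

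**The plan's own figure.** SAP 6.1 gives about 80% probability of at least one occurrence among 6 active subjects at 24% incidence. Check: 1 − 0.76^6 = 0.807, so it reproduces.

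**Illustration 1: one missed subject in a full cohort.**
- Change in rate: 1/6 − 0/6 = 16.7 percentage points.
- Exact (Clopper-Pearson) two-sided 95% upper limit for 0/6: 1 − 0.025^(1/6) = 45.9%.
- The same limit for 1/6: 64.1%.

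**Illustration 2: detection probability.** Carry the 24% over to a measured abnormality, and let u be the share of affected subjects whose abnormality appears only on unscheduled tests. The documents do not give u, so it is an assumption. The probability that a scheduled-only count shows at least one case among 6 is 1 − [1 − 0.24(1 − u)]^6:

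| u (assumed) | Probability |
|---|---|
| 0% | 80.7% |
| 10% | 76.8% |
| 25% | 69.6% |
| 50% | 53.6% |

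With all post-dose values counted, it stays at 80.7%.

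**What was actually dosed (SAP 7.1).** A1 to A4 had 8 subjects each, A5 had 4 and B1 had 2, so 4 × 8 + 4 + 2 = 38. The six-subject illustration fits A1 to A4. A5 has at most 4 active subjects, so one subject there is at least 1/4 = 25 points. For Part B, SAP 7.1 plans summary tables only for disposition, demographics and adverse events, with the rest in listings, so the shift-table point concerns Part A.

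**The case against.** The best defence is that little is hidden. Unscheduled values are listed, and out-of-range laboratory values have their own listing (SAP 17.1.3). A laboratory result judged clinically significant must be recorded as an adverse event (Protocol 8.5.2.1.6 and 8.5.2.4), as must significant worsening on any safety assessment, whether or not the protocol requires it (Protocol 8.5.2.1.8). Such events are then counted by subject (SAP 17.1.1). With 38 dosed subjects and no formal hypothesis testing, a reviewer can read the listings. Scheduled-only summaries by time point are also sensible, because they keep denominators stable.

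Much of this stands, and it rules out several stronger readings that a reader might infer:

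- *That unscheduled abnormalities vanish from every safety count.* They do not. Adverse event tables and the component for SAE, death or discontinuation do not depend on SAP 8.1.5.
- *That ECG and vital-sign abnormalities drop out of shift tables.* Shift tables are planned for laboratory data only.
- *That the bias is always towards fewer abnormalities.* This holds for a count of any post-dose value. In a by-time-point table, excluding a normal repeat leaves an unconfirmed abnormality in place, which works the other way.
- *That using a repeated pre-dose value as baseline distorts change from baseline.* The last pre-dose value is also the protocol's baseline (Protocol 9.4.2.2 and 9.4.2.3), and nothing in the documents shows a distortion.
- *That the stopping rules are weakened.* Confirmation by repeat in Protocol 8.3.5.5 operates during dosing and is not governed by SAP 8.1.5.

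The defence does not restore the endpoint. An adverse event record generally rests on the investigator's judgement of significance or on a consequence for treatment, whereas the endpoint counts potentially significant changes. Ordinary adverse events lie outside the primary endpoint by SAP 5.1.1. A listing is not a number and percentage of subjects.

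**Conclusion.** The point holds in a limited form. SAP 8.1.5 and the second primary safety component in SAP 5.1.1 conflict: applied as written, the rule leaves out a subject whose only qualifying value is unscheduled. The laboratory shift table likewise omits unscheduled abnormalities.

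The effect on the primary count is inferred from the general rule, because the SAP has neither criteria nor an output for that count. That gap is more basic than 8.1.5, and both should be closed together.

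The frequency cannot be derived from the documents. The 16.7 points, and the limits of 64.1% against 45.9%, show what one missed subject would mean in a full cohort; they do not estimate the loss. The conclusion assumes that a subject counts on any single qualifying post-dose value, and that an off-schedule repeat is an unscheduled measurement, as the pairing of the two terms in SAP 8.2.1 suggests. The change is worth making because the data already exist.

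**What to change.** 1. Limit the exclusion in SAP 8.1.5 to by-time-point summaries and changes from baseline.
2. State criteria for potentially clinically significant ECG, vital-sign and laboratory values. Fix them before unblinding, which SAP 3.0 already ties to an approved SAP.
3. Add to SAP Appendix 4 a table with the number and percentage of subjects meeting those criteria, by treatment, counting any post-dose value, scheduled or unscheduled, from first dose through follow-up.
4. Add a baseline-to-worst-post-dose shift for laboratory parameters, beside the scheduled-time shift table.

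The cost is the work of setting the criteria and some extra programming; no new data are needed. One downside remains: subjects tested more often have more chances to be counted. The new table should therefore mark counts that rest only on unscheduled values.
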